3.3. Randomisation

A team from the University of Kent will conduct the randomisation, operating independently from the evaluation team at Ipsos UK. The University of Kent will be provided with a list of schools without school names but marked with ID codes, ensuring they cannot discern the

schools' identities, thus maintaining blindness during the randomisation procedure. As a cluster trial, schools will be randomly allocated to the treatment or control group after screening (see section 3.4 below for the inclusion/exclusion criteria).

Simple randomisation balances confounding factors and provides unbiased average estimates (Morgan & Rubin, 2012). However, within a specific experiment, an uneven distribution of covariates might persist – both observed and unobserved – even after randomisation. Disproportionate distribution of crucial covariates among treatment groups can impact the analysis and interpretation of outcomes. While adjusting for this *post hoc* is possible, this method is less efficient than achieving balanced groups from the outset. Furthermore, it is not feasible when all individuals with specific characteristics are assigned to a single treatment group (Bruhn & McKenzie, 2009).

One approach to address this imbalance is randomising through minimisation which conduct the randomisation stratifying on one or more variables. In its simplest form, minimisation involves creating groups based on sampling variables and other relevant measures related to student achievement. In the current study context, schools are randomly assigned based on whether they are above or below the median proportion (%) of pupils with FSM6 (Median and below, above Median). The FSM6 indicator captures the history of pupils' eligibility for free school meals⁶.

Initially, the plan was to randomise using FSM6 in conjunction with school geographic locations. However, with the increasing number of eligible trial areas and strata included to ensure adequate recruitment, there was a significant decrease in the number of schools per stratum. As Roberts and Torgerson (1998) discussed, stratification is more efficient when the number of strata decreases. Consequently, the geographic area as a factor was dropped, relying only on FSM6 for randomisation, ensuring a more efficient approach.

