The randomisation process underwent a minor amend, now conducted in two batches, to provide schools ample time to implement the survey, thus maximising response rates and statistical power. The initial batch took place in early December 2023, involving schools that completed baseline testing by that time, while the second batch occurred in early January 2024, encompassing the remaining schools that completed baseline testing throughout December and January.

⁶ This refers to the situation when a student holds a historical FSM status. Following their FSM eligibility end date, they will retain the "Ever 6 FSM" classification for the subsequent six years. To illustrate, if a student was eligible for FSM from 1st September 2018 until 31st October 2020, their Ever 6 FSM status will continue until 31st October 2026, encompassing a 6-year duration beyond their FSM end date.

The randomisation process is blind to both the evaluation and the delivery team. The delivery team will be informed of the allocation to initiate the training.

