2.1 Design overview

This efficacy trial adopts a two-arm, two-level design with pupils clustered into schools. The unit of randomisation is the school. All pupils in Year 8 in the participating schools undertake baseline tests from November 2023 to January 2024 and outcome tests at the follow-up stage in March 2025. The schools within the control group continue to function according to business-as-usual. There is no waitlist design in this trial.

The randomisation process adopts the minimisation approach considering whether the percentage of students eligible for free school meals (FSM6) at each school fell above or below the median percentage of FSM6 across all schools in the sample. More detail is discussed in the next section.

The randomisation process was executed by colleagues from the University of Kent, operating independently from the evaluation team at Ipsos UK. The University of Kent was provided with a list of schools without school names but marked with ID codes, ensuring they could not discern the schools' identities, thus maintaining blindness during the randomisation procedure. The randomisation procedure occurred in two phases: one in early December 2023 and another in January 2024. Initially, the intention was to conduct baseline testing for

all schools in November and proceed with randomisation in December. However, extending the timeline became imperative to accommodate additional time for recruitment, data collection, fieldwork, and the constraints posed by the Christmas break and Ofsted inspections, allowing schools ample opportunity to implement the surveys.

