The primary outcome is externalising behaviour at pupil level in Year 8 measured by the Strengths and Difficulties Questionnaires (SDQ) – Combined Conduct and Hyperactivity Scale. There is a baseline measurement before the start of the intervention and then a follow-up measurement once the intervention ends, namely, 15 months after randomisation. The secondary outcomes at pupil levels in Year 8 consist of internalising behaviour, prosocial behaviours, total difficulties, non-psychotic psychological distress, well-being, sense of connectedness, exclusions and suspensions, and school attendance. Other secondary outcomes at the school staff level are attitudes related to TIC, school staff's well-being, school staff retention and sickness. Finally, the % of exclusions, suspensions and attendance of CYP at the school level will be collected. Detailed instruments for each outcome are described in Table 1 below.

Table 1 Summary of trial design

Trial design		Two-arm and cluster randomised at the school level
Unit of randomisation		School
Stratification variables (if applicable)		Binary indicator of school-level percentage of pupils eligible for Free School Meals (Below median percentage vs. At or above median percentage)
Primary outcome	variable	(CYP) Externalising behaviour
	measure (instrument, scale, source)	SDQ – Combined conduct and hyperactivity scale scores (0-20) (Survey)
Secondary outcome(s)	variable(s)	(CYP) Internalising behaviour
		(CYP) Prosocial behaviour
		(CYP) Total difficulties
		(CYP) Non-psychotic psychological distress

		
(CYP) Well-being
 
(CYP) Sense of connectedness
 
(CYP) Exclusions & suspensions
 
(CYP) School attendance
 
(School staff) Attitudes related to TIC
 
(School staff) Well-being
 
(School) Staff retention
 
(School) Staff sickness
 
(School) Exclusions & suspensions of CYP
 
(School) School attendance of CYP

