2.3.1 Primary outcome analysis

The primary outcome combines the Conduct Problems and Hyperactivity sub-scales of the Strengths and Difficulties Questionnaire (SDQ) to measure externalising behaviours.

We will employ a two-level multilevel model to account for the clustered nature of our data, where students are nested within schools. This modelling approach assumes that the schools included in the study represent a random sample from the broader population of schools. Multilevel models are well-suited for analysing hierarchical data structures and appropriately handling the variability within schools (among students) and between schools in terms of

outcomes. These models can effectively capture and model the complex sources of variation at multiple levels of the hierarchy (Bosker & Snijders, 2011).

The two-level **random-intercept model** is described by:

$$Y_{ij} = \beta_1 + TISUK_j\tau + (Baseline_{ij})\beta_2 + FSM_j\beta_3 + \mu_j + \varepsilon_{ij}$$

- Y_{ij} is the outcome for pupil i in school j ;
- $TISUK_j$ is a binary variable denoting whether a school is assigned to the intervention (1) or the control (0);
- $Baseline_{ij}$ represents pupil-level pre-test covariates and demographic characteristics at baseline for pupil i in school j .
- FSM_j is a binary indicator denoting whether a school is above the median proportion of FSM6 (1) or below (0).
- μ_j are the school level residuals [$\mu_j \sim i. i. d N(0, \sigma_\mu^2)$]
- ε_{ij} are the individual level residuals [$\varepsilon_{ij} \sim i. i. d N(0, \sigma_\varepsilon^2)$]

This is a random intercept model because $\beta_{1j} = \beta_1 + \mu_j$ corresponds to the school-level intercept for school j and $\beta_{1j} \sim i. i. d N(\beta_1, \sigma_\mu^2)$. The total variance is decomposed into two portions: the between-school variance (μ_j) and the within-school variance (ε_{ij}). The target parameter of the intervention is the average effect on pupil outcomes captured by τ .

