2.3.2 Secondary outcome analysis

The remaining secondary outcomes at the pupil and school staff levels follow the same equation as above. Secondary outcomes measured at the school level will be estimated using linear regression (ordinary least squares, OLS) with robust standard errors to account for potential heteroscedasticity. Since there is only one observation per school for school-level outcomes, clustering at the school level is not applicable, and robust standard errors are used to ensure valid statistical inferences in the presence of heteroscedasticity.

The **school-level model** is a linear regression set out by:

$$Z_j = \gamma_0 + \gamma_1 Intervention_j + \gamma_2 BaseS_j + \gamma_3 FSM_j + \mu_j$$
$$\mu_j \sim N(0, \sigma_\mu^2)$$

Where:

- Z_j is the outcome at the school level;
- γ_0 is the intercept;
- *Intervention* is a binary variable that equals 1 if school is within intervention arm and 0 otherwise;
- $BaseS_j$ represents the baseline covariate at the school level, which is centred around the grand mean of the school level;
- FSM_j is a binary variable indicating whether a school's % proportion of FSM pupils is above or below the median in the sample of schools participating in the trial;
- μ_j is the random error across all school
- σ_μ^2 is the residual/error variance between schools

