3.4.1 Primary analysis

The primary analysis will likely be a linear regression model adjusted for baseline stratification covariates (proportion FSM), and the baseline value of the outcome. As there is variation in

business as usual (BAU) across sites, a multilevel model will be estimated to account for pupils being nested within schools. Individual outcomes will be incorporated into the model with an inverse propensity weight for each participant.

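### School-level FSM6 enters the main-trial models only as a median split; adding the percentage already held would give a small, conditional gain in precision

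*Protocol*

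**What the plan says.** **The cut.** Protocol 3.3 randomises schools by "whether they are above or below the median proportion (%) of pupils with FSM6 (Median and below, above Median"), so a school exactly at the median falls in the lower group. SAP Table 1 (section 2.1) gives "Below median percentage vs. At or above median percentage", which puts that school in the upper group, and names free school meals without specifying FSM6. The text of SAP 2.1 says only that a school "fell above or below the median percentage of FSM6 across all schools in the sample".

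**The models.** In the primary model (SAP 2.3.1) the FSM term "is a binary indicator denoting whether a school is above the median proportion of FSM6 (1) or below (0"). In the school-level regression (SAP 2.3.2) it "is a binary variable indicating whether a school's % proportion of FSM pupils is above or below the median in the sample". The Stata line has a single `fsm` term, and a footnote in SAP 2.3 confirms that the stratification covariate is binary. No main-trial equation contains the school's FSM6 percentage. SAP Table 5 also lists pupil-level sex and FSM status for the pupil outcomes.

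**The draws.** Randomisation was in two batches. Of the first, protocol 3.3 says: "The initial batch took place in early December 2023, involving schools that completed baseline testing by that time". Of the second: "the second batch occurred in early January 2024, encompassing the remaining schools that completed baseline testing throughout December and January". Neither document says which schools' values set the median at each draw.

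**The concern.** A school's FSM6 percentage is a baseline value that the trial holds for every school. Cutting it at the median treats a school just above the median like the most deprived school in the sample, and a school just below it like the least deprived. If deprivation predicts externalising behaviour between schools, the discarded part stays in the school-level residual, which is a large component of the error of a cluster trial.

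Stratifying on halves also balances only halves. A chance difference between arms in FSM6 within a stratum is neither prevented by the allocation nor removed by the model, and SAP Table 6 would not show it because it reports only the binary. At stake is a little precision in the primary and school-level analyses, and adjustment for that residual imbalance. The validity of the planned estimate is not in question.

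**Working it through.** **Inputs.** From SAP Table 4, randomisation column: 40 intervention and 38 control schools, m = 166 pupils per school, ICC ρ = 0.015, two-sided alpha 0.05, power 0.8. From SAP Table 6: 19 of 38 control and 20 of 40 intervention schools above the median. Assumed, because the documents give no figure: R2, the share of the remaining school-level variance that FSM6 explains.

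**1. The plan's own figure.** MDES = M × √[(ρ + (1−ρ)/m) / q], with q = 40×38/78 = 19.49.
- The bracket is 0.015 + 0.985/166 = 0.015 + 0.00593 = 0.02093.
- With normal M the MDES is 0.0918. With t on 76 df it is 0.0930. The stated figure is 0.094, so it is reproduced to about 1% with t.
- The protocol's 0.1064 (100 schools, m = 160, ρ = 0.03) is reproduced exactly with normal M.
- Before any covariates, the between-school share of error variance is 0.015/0.02093 = 72%.

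**2. Information kept by a median split.** The squared correlation between a variable and its median split is 2/π = 0.64 for a normal variable, 0.75 for a uniform one and 0.48 for an exponential one. Under normality 36% is discarded.

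**3. Gain from adding the percentage.** The variance of a school mean is 0.015(1 − 0.637·R2) + 0.00593 with the split alone, and 0.015(1 − R2) + 0.00593 with the percentage added. At R2 = 0.2:
- split alone: 0.01309 + 0.00593 = 0.01902
- with percentage: 0.01200 + 0.00593 = 0.01793
- ratio of SEs: √(0.01793/0.01902) = 0.971, a 2.9% reduction.

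This formula ignores the small cost of estimating one more coefficient when the arms differ by chance on the new covariate. That adds about 1/75 to the variance, or √(1 + 1/75) = 1.0066 on the SE. Three separate simulation runs (78 schools, allocation stratified by the split) include this cost and give the last column.

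| Assumed R2 | SE reduction, formula | less 0.7% cost | simulation |
|---|---|---|---|
| 0 | 0 | −0.7% | −0.5 to −0.8% |
| 0.05 | 0.7% | 0.0% | about 0 |
| 0.1 | 1.4% | 0.7% | 0.6 to 0.9% |
| 0.2 | 2.9% | 2.3% | 2.0 to 2.5% |
| 0.3 | 4.6% | 4.0% | 3.5 to 3.8% |
| 0.5 | 8.8% | 8.2% | 7.5 to 8.3% |

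Across 48% to 75% of variance kept, the formula gain at R2 = 0.2 runs from 4.1% to 2.0%. If baseline scores are assumed to explain half the school variance and 40% of the pupil variance, and FSM6 explains 20% of the school variance then left, the formula gain is 2.7% (MDES 0.0647 to 0.0629).

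**4. Residual imbalance.** Within strata the FSM6 variance is 1 − 0.637 = 0.363 school SDs squared. The SD of the arm difference is √[0.363 × (1/40 + 1/38)] = 0.14 school SDs. About 5% of allocations would exceed 1.96 × 0.14 = 0.27 in either direction.

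**5. Does the differing cut move a school?** Table 6 counts 19 + 20 = 39 of 78 schools above the median, exactly half. If the median is that of these 78 schools, or is taken within each batch, exactly half strictly above means that no school sits at the median. Both definitions then give the same strata. They could differ only if the median came from another set of schools, for example the first batch's median carried forward.

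**The case against.** The strongest reply is that adjusting for the stratification factor as randomised is a valid, pre-specified model and that the gain is small and unproven. SAP 2.2 intends mean-centred baseline scores at both pupil and school level, SAP 2.3.2 includes each school's own baseline outcome, and Table 5 lists pupil FSM status. These may already carry much of the deprivation gradient, and the 72% in step 1 is a figure before such adjustment. SAP 2.3.4 also allows for balance checks and a possible covariance-adjusted robustness model. All of this stands, and it is why the gain must be read against the R2 left after the other covariates. It does not remove the point, because school-level FSM6 is still dichotomised in every main-trial equation and the robustness model is only something the team may consider.

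Four stronger readings are tempting, and the documents do not support them.
- **That the median was not yet fixed at the first draw.** The batches are defined by completion of baseline testing, whereas FSM6 is a school characteristic that could have been known earlier. SAP 2.1 does mention extra time for recruitment, so the matter is open, but no text settles it.
- **That some schools sit in the wrong stratum.** Any count of such schools has to assume batch-specific medians later replaced by an overall one. Nothing documents that, and Table 6 gives no sign of it.
- **That FSM6 is the only school-level prognostic variable held.** The school-level baseline scores contradict this.
- **That the QED already uses the continuous value.** SAP 3.4.1 is "adjusted for baseline stratification covariates (proportion FSM"), but SAP 3.4.4 calls the factor a binary indicator and protocol Appendix 2 specifies the median split for the same analysis. The phrase is shorthand.

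**Conclusion.** The point holds as an optional improvement. The main-trial equations discard about a third of the information in a percentage the trial holds (36% if FSM6 is normal, 25% if uniform, 52% if exponential). Recovering it is likely to be worth between nothing and about 4% of the standard error for an R2 of 0.05 to 0.3. Larger gains need FSM6 to explain around half of the school variance left in the model, which nothing in the documents supports. If FSM6 explains none of it, the change costs under 1%. These figures rest on an assumed R2, a linear relation and the ICC of 0.015. No conclusion about power depends on them, since the stated MDES of 0.094 is well below the required 0.20.

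The two definitions of the cut do contradict each other, but on Table 6 this is probably a matter of wording and not of classification.

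**What to change.** **Model.** In SAP 2.3.1, the Stata line and SAP 2.3.2, keep the stratum indicator as stored at each draw and add the school's FSM6 percentage as a continuous covariate centred at the grand mean. Make the amendment before follow-up data are seen. If they have already been seen, report the extended model as a labelled sensitivity analysis. The cost is one degree of freedom (75 to 74 at school level, about 0.02% of MDES through the critical value alone), the chance-imbalance cost of about 0.7% of the SE already counted above, a linearity assumption, and a short SAP amendment. No new data are needed.

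**Wording.** Align SAP Table 1 with the protocol's cut (median and below versus above), label the variable FSM6 throughout, and state which schools' values set the median at each of the two draws.

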3.4. Participants

Recruitment for the trial will be managed by the delivery team and done at the school level, according to the following recruitment activities:

- Contacting virtual heads and local authority mental health leads who have expressed an interest in trauma-informed training in areas where TISUK have not run courses.
- Attending virtual head meetings to give an outline of the project.
- Encouraging partners who express interest to create links/share with contacts in neighbouring regions to increase the recruitment scope.
- Distributing briefing notes/information sheets through partners in these areas asking for EOI from schools.
- Schools are invited to attend regular online information briefings to find out more about TISUK.

Three 1.5-hour project specific information briefings held in July 2023.

The delivery team will focus recruitment efforts on those schools that expressed interest in the trial.

Eligible schools to the trial must satisfy the following **inclusion criteria**:

- Located within the target area⁷

Schools will not be selected if they meet any of the below **exclusion criteria**:

- Schools should not have a staff member who has completed the TISUK 11-day diploma
- Schools should not have received TISUK whole staff training in the last three years.

⁷ The target includes the following areas: Greater Manchester, Greater London, West Midlands, Gloucestershire, Somerset, Bristol, West Yorkshire, South Yorkshire, Merseyside, Tyne and Wear, East Sussex, Norfolk, Northumberland, Bedfordshire, Hertfordshire, Cambridgeshire, East Riding of Yorkshire, Darlington, Northamptonshire, Lincolnshire, Essex, Cheshire, Leicestershire, Bournemouth, Christchurch and Poole, Southampton, Kent, Shropshire, Devon, Bolton, Kingston upon Hull, Herefordshire, Wiltshire, Surrey, Hampshire, North Yorkshire, Derby, Swindon, Nottinghamshire

- If a member of staff has completed TISUK SLT or SMHL training, then they should not have made changes to policy or wider staff practice within the school (e.g., staff training around PACE).
- Schools should not have received intensive training around TIP and implementation from a different provider within the last three years.
- Be a fee-paying school
- Be alternative provision or special schools with 'SEMH' focus.

The delivery team will focus recruitment efforts in the above three locations although additional areas may be considered if the number of schools recruited does not reach the desired sample size.

There are two levels of participation for CYP in the intervention arm of the study. At a whole school level, the intervention targets school staff who will implement structural changes in policies and practices that ultimately impact all CYP in that school. Outcomes will be measured for a single-year group (Year 8).

At a targeted level, one aspect of the intervention involves training diploma practitioners who will target a sub-group of CYP across the school with a trauma history and provide tailored support. This sub-group of CYP is made up of children who already receive targeted support within the school and so will continue to do so but making use of new skills and knowledge provided by the intervention. Additionally, the measurement tools diploma delegates access through TISUK sessions (ACEs/resilience questionnaire/developmental deficit and gang affiliation checklists and school bonding survey) are integrated into this process.

As this population is only identified in intervention schools, a study within a trial (SWAT) will be undertaken focussing on those identified for this additional support who are in Year 8 (and so are already included in the outcomes measurements for the trial). As the control group cannot be randomised, a quasi-experimental design is appropriate creating a control group using a propensity score matching (PSM) approach. Section 4.1 and Appendix 2 discuss this in detail.

3.5. Sample size calculations

The sample sizes presented in Table 4 have been calculated using Stata 17© according to the following assumptions:

1. No pre-post correlations are assumed as there are no reliable sources of these for externalising behaviours and estimating them would add uncertainty to the final

sample size calculation. By omitting this parameter, we obtain a conservative estimate of sample size for an analysis of covariance.

2. The adolescent population SDQ (externalising scale) mean is 6.0 and the assumed pooled Standard Deviation (SD) is 1.74⁸, using the UK self-report population norms for 11-15 year olds⁹. Thus, to detect an effect size of 0.2 or greater we need a SDQ externalising behaviours score difference of 6.0 (control) versus 5.66 (intervention). This difference requires 527 participants in each group, 1,054 for the whole sample.
3. Assuming 10% pupil-level attrition between baseline and follow-up requires a total sample size of 1,172.
4. Following Shackleton, Hale, Bonell, and Viner (2016) and Parker, Nunns, Xiao, Ford, and Ukoumunne (2021), with an ICC of 0.03 and a harmonic mean year group of 200 pupils, based on the average year group size in England of 197 (ONS, 2023) of whom 80%, 160, will consent to participate, the design effect is 5.8 (1+(0.03*160)), which inflates the sample to 6,798 (5.8*1,172).
5. Given assumptions 1 to 4 above, we need a minimum of at least 25 schools in each arm for an efficient cluster trial, that is 50 schools in total. Nevertheless, we propose double the sample size aiming to recruit 100 schools with 50 on each arm. The rationale for this is further discussed below. Table 2 provides an overview of the numbers available at the primary endpoint for a variety of school retention rates (100%, 90%, 80%, 70%, 60%) and pupil retention rates (100%, 90%, 80%, 70% and 60%) scenarios. In all scenarios the numbers recruited and followed up are sufficient to meet the sample size requirements when we account for the different design effects (i.e., as more pupils drop out, the design effect, which is a function of the cluster size, decreases, hence the overall sample size decreases).

Table 2 Impact of different pupil and school retention rates on sample size

		Proportion of pupils retained				
		100%	90%	80%	70%	60%
Number of schools retained	100	16,000	14,400	12,800	11,200	9,600

⁸ The SD has been estimated as the standardised SD using the same raw data for both scales

⁹ <https://www.sdqinfo.org/norms/UKNorm1.pdf>

	90	14,400	12,800	11,200	9,600	8,640
	80	12,800	11,200	9,600	8,640	7,680
	70	11,200	9,600	8,640	7,860	6,720
	60	9,600	8,640	7,860	6,720	5,760

Table 3 Impact of different pupil and school retention rates on MDES

		Proportion of pupils retained				
		100%	90%	80%	70%	60%
Number of schools retained	100	0.1064	0.1074	0.1086	0.1102	0.1122
	90	0.1122	0.1132	0.1145	0.1161	0.1183
	80	0.1190	0.1201	0.1214	0.1232	0.1255
	70	0.1272	0.1284	0.1298	0.1317	0.1341
	60	0.1374	0.1385	0.1402	0.1422	0.1449

Several considerations come into play to target 100 schools and 16,000 young people. First, a larger pool of schools increases the likelihood of recruiting a diverse population of school types (e.g., school-level of deprivation, FSM, different socioeconomic backgrounds) and student demographics, enabling robust subgroup analyses and generalizability of findings across various contexts. Second, a large overall sample size enhances statistical power to detect smaller but potentially meaningful intervention effects, minimising the risk of false negatives and providing reliable findings to inform future interventions. Third, the target sample size was selected to ensure sufficient power for the quasi-experimental design (QED) analysis focused on a targeted subgroup of students. Lastly, a larger sample size accommodates the cluster randomised trial design, accounting for potential clustering effects and maintaining adequate power for the primary analysis.

The sample size calculation has also considered **the trade-off between internal/external validity and ethical considerations**. Thus, outcomes will be measured on a specific cohort rather than the whole school population to minimise the burden on schools, school staff, and students while achieving efficient data collection. Through co-production workshops with teachers and a youth advisory board, the Year 8 cohort (2023/2024) was carefully selected as the appropriate group for measurement.

Table 4 Sample size calculations

		Scenario 1
Minimum Detectable Effect Size (MDES)		0.1064
Pre-test/ post-test correlations	level 1 (participant)	n/a
	level 2 (cluster)	n/a
Intracluster correlations (ICCs)	level 1 (participant)	n/a
	level 2 (cluster)	0.03
Alpha		0.05
Power		0.8
One-sided or two-sided?		2
Average cluster size (if clustered)		160¹⁰
Number of clusters	Intervention	50
	Control	50
	Total	100

¹⁰ Average school size in England is 986, average year size is 200 and accounting for a potential 20% not consenting, hence, cluster size 160.

		Scenario 1
Number of participants	Intervention	8,000
	Control	8,000
	Total	16,000

4. Outcome measures

The impact of the intervention is measured through a primary outcome at the CYP level, the combined conduct and hyperactivity scale scores from the Strengths and Difficulties Questionnaire (SDQ) at CYP level, and a list of secondary outcomes at CYP, school staff and school level. Table 5 sets out the primary and secondary outcomes.

Table 5 Primary and secondary outcomes

Outcome	Primary / Secondary	Level	Scales of instrument	Description and source
Externalising behaviours	Primary	CYP	SDQ – combined conduct and hyperactivity scales (0-20)	The Strengths and Difficulties Questionnaire (SDQ) is a brief questionnaire designed to assess behavioural patterns in children and adolescents aged 3-16. It consists of 25 items covering various psychological attributes, including positive and negative aspects. YEF utilises the Strengths and Difficulties Questionnaire in all its projects (where appropriate) to ensure uniformity and facilitate comparisons across various evaluations. Further information about the SDQ is available here: https://www.sdqinfo.org/ .

Outcome	Primary / Secondary	Level	Scales of instrument	Description and source
				Data will be collected electronically by the evaluation team (Ipsos) using Dimensions ¹¹ .
Internalising behaviour	Secondary	CYP	SDQ – combined emotional problems and peer problems scales (0-20)	SDQ Data will be collected electronically by the evaluation team (Ipsos) using Dimensions.
Prosocial behaviour	Secondary	CYP	SDQ – Prosocial behaviour scale (0-10)	SDQ Data will be collected electronically by the evaluation team (Ipsos) using Dimensions.
Total difficulties	Secondary	CYP	SDQ – Total score (sum of internalising and externalising behaviours scales (0-40))	SDQ Data will be collected electronically by the evaluation team (Ipsos) using Dimensions.
Non-psychotic psychological distress	Secondary	CYP	General Health Questionnaire (GHQ-12) ¹² - total score, depression, anxiety and	The self-administered questionnaire serves to identify non-psychotic and minor psychiatric disorders. Clinicians widely employ it as an initial screening method for assessing individuals within the general population and in a community or non-psychiatric clinical settings such as primary care or general medical outpatient facilities. Suitable for

¹¹ Dimensions is a software developed by Ipsos to conduct surveys, similar to Qualtrics.

¹² Goldberg D, Williams P. A user's guide to the General Health Questionnaire. Windsor: NFER-Nelson; 1988

Outcome	Primary / Secondary	Level	Scales of instrument	Description and source
			confidence sub-scales	adolescents and adults, the questionnaire consists of 12 questions. Data will be collected electronically by the evaluation team (Ipsos) using Dimensions.
Children's well-being	Secondary	CYP	Short Warwick Edinburgh Mental Well-being Scale ¹³	The SWEMWBS is a shortened version of the Warwick-Edinburgh Mental Well-being Scale (WEMWBS) that was created to facilitate the monitoring of mental well-being within the general population. It is also used to assess the effectiveness of projects, programs, and policies to enhance mental well-being. The SWEMWBS comprises seven out of the 14 statements found in the WEMWBS, explicitly focusing on thoughts and feelings related to functioning rather than pure emotions. The seven statements in the SWEMWBS are phrased positively and offer five response options ranging from "none of the time" to "all of the time." Children and young individuals are requested to reflect on their experiences over the past two weeks. More info on SWEMWBS is available at https://www.corc.uk.net/outcome-experience-measures/short-warwick-edinburgh-mental-wellbeing-scale-swemws/ Data will be collected electronically by the evaluation team (Ipsos) using Dimensions.

¹³ Clarke, A., Putz, R., Friede, T., Ashdown, J., Adi, Y., Martin, S., Flynn, P., Blake, A., Stewart-Brown, S. & Platt, S. (2010). Warwick-Edinburgh mental well-being scale (WEMWBS) acceptability and validation in English and Scottish secondary school students (The WAVES Project). NHS Health Scotland; <http://www.healthscotland.scot/media/1720/16796-wavesfinalreport.pdf>.

Outcome	Primary / Secondary	Level	Scales of instrument	Description and source
Sense of connectedness (ERQ5)	Secondary	CYP	School Connectedness Scale ¹⁴	
The scale consists of 10 items designed to evaluate the interpersonal connection individuals experience within their social environment. Participants rate their responses on a Likert scale, ranging from 1 (strongly disagree) to 6 (strongly agree). This tool will measure the sense of belonging at the school level.
 
More information on this instrument is available here: https://doi.org/10.1007/s12187-020-09726-8
 
Data will be collected electronically by the evaluation team (Ipsos) using Dimensions.

Percentage of exclusions, suspensions and attendance	Secondary	CYP	% of each indicator at CYP level	This will be collected through the SIMS or a similar database recorded by schools.
Attitudes related to TIC	Secondary	School Staff	Attitudes Related to Trauma Informed Care (ARTIC-45)	
The ARTIC is a psychometrically valid Trauma-Informed Care (TIC) measure documented in peer-reviewed literature. Its development emerged through a collaborative effort between the Traumatic Stress Institute of Klingberg Family Centers and [name] from Tulane University. The primary objective of the ARTIC is to assess the positive or negative attitudes of service providers towards TIC. It operates on the foundational belief that staff attitudes significantly influence their behaviours, and the real-time behaviours of staff play

¹⁴ Lee, R. M., Draper, M., & Lee, S. (2001). Social connectedness, dysfunctional interpersonal behaviors, and psychological distress: Testing a mediator model. *Journal of Counseling Psychology*, 48(3), 310.

Outcome	Primary / Secondary	Level	Scales of instrument	Description and source
				
a pivotal role in the successful implementation of TIC. What sets ARTIC apart is its unique approach. While numerous self-assessment tools have been designed to evaluate organisational aspects of TIC implementation (such as screening, training, treatment models, and policies), the ARTIC focuses specifically on measuring staff attitudes.
 
For more information on ARTIC see: https://www.traumaticstressinstitute.org/the-artic-scale/
 
Data will be collected electronically by the evaluation team (Ipsos) using Dimensions.

Staff well-being	Secondary	School staff	Short Warwick Edinburgh Mental Well-being Scale	See above on the same measure for CYP
Proportion of school staff retention	Secondary	School	Staff retention rate as a percentage of total staff	This will be collected through the SIMS or a similar database recorded by schools
Proportion of staff sickness	Secondary	School	Staff sickness rate as a percentage of total staff	This will be collected through the SIMS or a similar database recorded by schools
Number of exclusions	Secondary	School	CYP exclusion rate as a percentage of total CYP	This will be collected through the SIMS or a similar database recorded by schools

Outcome	Primary / Secondary	Level	Scales of instrument	Description and source
Number of suspensions	Secondary	School	CYP suspension rate as a percentage of total CYP	This will be collected through the SIMS or a similar database recorded by schools
Number of attendance	Secondary	School	CYP attendance rate as a percentage of total CYP	This will be collected through the SIMS or a similar database recorded by schools

We will measure primary and secondary outcomes at CYP, staff and school levels at baseline. The follow-up data collection of all primary and secondary outcomes will happen 15 months after baseline data collection to allow outcomes to become apparent, namely, in the post-intervention stage. This is expected to occur in March-April 2025.

Surveys will be administered to pupils via an online survey link using Ipsos’s survey software (Dimensions) sent to schools during baseline and follow-up data collection periods. School staff will be supported in the administration of the survey via our **School liaison officer** who will provide detailed instructions on the administration procedure, respond to questions and provide technical support as required.

Schools will be asked to administer the survey to the target year group (Year 8) in whole class, or smaller, groups in ICT or computer rooms with one child allocated to each computer. A member of school staff will be present throughout and provide short instructions (script provided) before and after the surveys are complete. Paper copies will be provided on request for those who need them. The survey will take approximately 15 minutes to complete.

The survey link will include an introductory page highlighting confidentiality, right to withdraw and data protection procedures written in accessible and child-friendly language. Each pupil will be asked for their assent to take part by providing their name and class name before clicking through to the start of the survey. Name/class information, date of birth, ethnicity and sex will be used to match baseline and follow-up data and identify Unique Pupil Number.

Data on staff well-being and attitudes to trauma will be gathered through a survey. Staff will be asked for their consent to take part before starting the survey. The **administrative records** will be gathered from schools coordinated by our School liaison officer accessing SIMS or any other corresponding database managed by schools at baseline and at the end of the intervention, corresponding to two academic years.

